		
Exploratory objective related to banked biospecimens was removed.
 
Section 8.3 Adverse events and Serious Adverse Events
 
Appendix 3 Adverse Events: Definitions and Procedures for Recording, Evaluating, Follow-up, and Recording.
 
Appendix 4 Contraceptive Guidance.
 
Appendix 10 Prohibited concomitant medications.
 
Changes made for improved instruction and process clarity:
 
Requirements for mental health professional assessments and recurrent suicidal ideation and behavior have been clarified.
 
The research supporting accelerometry has been described.
 
Added instruction for when to collect the eDiaries from participants.
 
Added instruction to clarify that banked biospecimens are collected for all participants (as local regulations and IRBs/ECs allow).
 
Dispensing and administration instructions for study intervention have been clarified.
 
Study-specific definitions of medication errors have been updated.
 
Tuberculosis testing procedures have been clarified.
 
Evaluation of hand eczema has been added to the rater qualifications and has been clarified.
 
Data collection requirements for adverse events of conjunctivitis have been added.

DOCUMENT HISTORY		
Document	Version Date	Summary and Rationale for Changes

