received placebo ($P < 0.001$ for both comparisons). In addition, in the 2 trials, an improvement from baseline to week 16 of at least 75% on the Eczema Area and Severity Index was reported in significantly more participants who received each regimen of dupilumab than in participants who received placebo ($P < 0.001$ for all comparisons). Dupilumab was also associated with improvement in other clinical end points, including reduction in pruritus and symptoms of anxiety or depression and improvement in quality of life. Injection-site reactions and conjunctivitis were more frequent in the dupilumab groups than in the placebo groups.¹⁷

In the CAFÉ study, the efficacy and safety of dupilumab in combination TCS was evaluated in 325 adults with inadequate response to/intolerance of cyclosporin A (CsA), or for whom CsA treatment was not medically advisable. In this 16-week, double-blind, randomized, placebo-controlled, Phase 3 trial, participants were randomized 1:1:1 to subcutaneous dupilumab 300 mg weekly (QW) or every 2 weeks (Q2W) or placebo. All received concomitant medium-potency TCS from Week -2 through Week 16; dosage could be tapered if lesions cleared or could be stopped for adverse reactions to TCS. Significantly more participants in the dupilumab QW + TCS and Q2W + TCS groups achieved $\geq 75\%$ improvement from baseline in the Eczema Area and Severity Index at Week 16 vs. the placebo + TCS group (primary endpoint) (59.1% and 62.6% vs. 29.6%, respectively; $P < 0.001$ vs. placebo + TCS, both doses). More participants in the dupilumab QW + TCS and Q2W + TCS groups achieved $\geq 90\%$ improvement from baseline in the EASI at Week 16 vs. the placebo + TCS group (post-hoc outcome) (37.3% and 45.8% vs. 12.0%, respectively). Other clinical outcomes and atopic dermatitis symptoms were significantly improved in the dupilumab QW + TCS and Q2W + TCS groups, including pruritus, pain, sleep disturbance, symptoms of anxiety and depression, and quality of life (QoL). Treatment groups had similar overall rates of adverse events (QW + TCS, Q2W + TCS and placebo + TCS groups: 69.1%, 72.0% and 69.4%, respectively) and serious adverse events (1.8%, 1.9% and 1.9%, respectively). Conjunctivitis was more frequent with dupilumab + TCS; skin infections were more frequent with placebo + TCS.¹⁸

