- All AEs regarding conjunctivitis, herpes zoster, and acne or folliculitis should have additional details collected.

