6.6.1. Adverse Events

The safety data will be summarized in accordance with CaPS. All safety data will be summarized descriptively through appropriate data tabulations, descriptive statistics, categorical summaries, and graphical presentations. Safety endpoints for the study include:

- Treatment-emergent AEs and SAEs;
- Withdrawals from active treatment due to AEs;

Adverse events of special interest are the following:

- Serious infections, defined as serious adverse events in System Organ Class Infections And Infestations;
- Herpes zoster defined by Customized MedDRA Queries.
- Conjunctivitis defined by Conjunctivitis details CRF page
- Acne and folliculitis defined by Acne and Folliculitis details CRF page

The incidence and severity of AE of special interest will be reported by System Organ Class and Preferred Term.

It should be recognized that most studies are not designed to reliably demonstrate a causal relationship between the use of a pharmaceutical product and an adverse event or a group of adverse events. Except for selected events in unique situations, studies do not employ formal adjudication procedures for event classification. As such, safety analysis is generally considered as an exploratory analysis and its purpose is to generate hypotheses for further investigation.

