Appendix 8.2.6. Adverse Event of Special Interest

- The following analyses will be provided for Acne
 - [1] Time of First Event, Probability of Resolution and Outcome of Treatment-Emergent Acne
 - [2] Summary of Treatment for First event of Treatment-Emergent Acne
 - [3] Individual listing of Treatment-Emergent Acne
 - [4] Individual listing of Treatment-Emergent Acne Details
- The AE page will be merged with Acne and Folliculitis details page by AE ID to identify Acne and Folliculitis respectively; AE page will be merged with Conjunctivitis details page by AE ID to identify conjunctivitis.
- Similar analyses [1] ~ [4] will be provided for Folliculitis.
- Similar analyses [1], [3] and [4] will be provided for Conjunctivitis
- Similar analyses [1] and [3] will be provided for serious infections and herpes zoster.

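### The SAP identifies conjunctivitis, acne and folliculitis for its special-interest outputs only through a linked details form, with no coded-term fallback or reconciliation

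*SAP*

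**What the plan says.** SAP 6.6.1 lists the adverse events of special interest in four bullets. Two are defined from data held on every AE record: "Serious infections, defined as serious adverse events in System Organ Class Infections And Infestations" and "Herpes zoster defined by Customized MedDRA Queries". The other two are defined by a supplementary form: "Conjunctivitis defined by Conjunctivitis details CRF page" and "Acne and folliculitis defined by Acne and Folliculitis details CRF page". Incidence and severity are then to be tabulated by MedDRA class and term.

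Appendix 8.2.6 shows how the form-based rule is to be programmed: "AE page will be merged with Conjunctivitis details page by AE ID to identify conjunctivitis". It gives the same instruction for acne and for folliculitis. Its outputs include time of first event, resolution, outcome and listings.

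On data collection, Protocol 8.2.1 says: "All AEs regarding conjunctivitis, herpes zoster, and acne or folliculitis should have additional details collected". The Amendment 2 entry in the document history (14 August 2020) records: "Data collection requirements for adverse events of conjunctivitis have been added".

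Protocol 8.3.8 marks AESIs as not applicable, so SAP 6.6.1 and Appendix 8.2.6 are the only places where these groups are defined.

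**The concern.** Under this rule an event enters the AESI outputs because a second form was completed and correctly linked, not because of what was reported and coded. If the page is missing, or carries the wrong AE ID, the merge does not find the event. Neither document says what to do then, and no planned step would show that it had happened.

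Conjunctivitis is where this matters most. The protocol's background reports it as more common on dupilumab than on placebo in several trials; of the trial in patients unsuited to cyclosporine it says "Conjunctivitis was more frequent with dupilumab + TCS". One of this study's safety objectives is to compare the two arms, and the AESI summary is where a reader will look for that contrast. If the AESI table and the general AE table can give different counts for the same event, with no planned reconciliation, the reader cannot tell which to trust.

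**Working it through.** The plan states no figure on this point, so there is none to reproduce. The check is a comparison of the text, followed by simple algebra for size.

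**1. The four definitions side by side (SAP 6.6.1)**

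| AESI | Found from | Needs a second form? |
|---|---|---|
| Serious infections | Seriousness plus system organ class | No |
| Herpes zoster | Customized MedDRA query | No |
| Conjunctivitis | Conjunctivitis details page | Yes |
| Acne and folliculitis | Shared details page | Yes |

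Protocol 8.2.1 asks for extra details for zoster in the same sentence as for the other three. For zoster, then, the plan already separates case finding from descriptive detail. It gives no reason for combining the two for the others.

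**2. Following one event through the outputs.** Take a treatment-emergent AE coded as conjunctivitis with no linked details page.

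- General safety summaries and listings (SAP 6.6 and 6.6.1): included, because they cover all treatment-emergent AEs.
- AESI incidence and severity (SAP 6.6.1): not included, because the definition is the page.
- Conjunctivitis analyses in Appendix 8.2.6: not included, because the merge by AE ID is what identifies the event.

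**3. Size.** Let p1 and p2 be the true risks in the two arms. Let m be the share of affected participants with no linked page, equal in both arms.

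- Counted risk in each arm = p × (1 − m)
- Counted difference = (1 − m) × (p1 − p2)
- Counted ratio = p1 / p2, unchanged

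The documents give neither m nor expected event rates for this trial. Both are assumed here for illustration: p1 = 10%, p2 = 3%, and m from 0 to 30%.

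| m | Counted risks | Difference (points) |
|---|---|---|
| 0 | 10.0% vs 3.0% | 7.0 |
| 5% | 9.5% vs 2.85% | 6.65 |
| 10% | 9.0% vs 2.7% | 6.3 |
| 20% | 8.0% vs 2.4% | 5.6 |
| 30% | 7.0% vs 2.1% | 4.9 |

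With the planned 300 per arm, the first row is 30 vs 9 participants. At m = 20% it is 24 vs 7.2, and (24 − 7.2)/300 = 5.6 points.

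**4. A possible source of missing pages.** The original protocol is dated 4 November 2019 and the conjunctivitis collection requirement came with Amendment 2. A conjunctivitis event recorded before a site adopted the amendment could lack the page. The documents do not say when the page went live, whether any such event occurred, or whether pages were completed retrospectively. This applies to conjunctivitis only.

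**The case against.** The best defence is that the page is intended for every such AE, so the page-based set and the reported set should coincide. Protocol 8.2.1 asks for details on all of them and also refers conjunctivitis AEs for an ophthalmology examination. Protocol 10.1.7 assigns data quality checks to the sponsor and source verification to monitors, and the eCRF may force the page or reconcile IDs; those specifications are not part of these documents. An investigator-completed page is a defensible case definition, and a term list has inclusion and exclusion errors of its own. The AESI summary is descriptive, SAP 6.6.1 treats safety analysis as generally exploratory, and Appendix 8 is not meant for the study report. All of this stands, and it limits the weight of the point. It does not supply the missing fallback or reconciliation.

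A reader might infer three stronger things that the documents do not support.

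- **That the event disappears from the arm comparison.** It does not; it remains in the general treatment-emergent tables and listings.
- **That undercounting is certain.** It requires m above zero, and nothing in the documents shows that it is.
- **That the loss would differ by arm.** Investigators and participants are blinded (Protocol 6.3.2) and allocation is 1:1 in blocks (Protocol 6.3.1). Gaps that depend on site or calendar time would be expected to fall on both arms. No mechanism for differential loss is stated.

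**Conclusion.** The point holds in a limited form. As written, the AESI counts for conjunctivitis, acne and folliculitis depend on completion and linkage of a second form, and the plan has no step that would detect a failure. The effect is confined to the AESI incidence and severity summary and the Appendix 8.2.6 analyses.

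Its size is proportional. With equal loss in both arms, the risk difference falls by the fraction m and the risk ratio is unchanged; with complete pages there is no effect. The percentage-point figures rest on assumed risks and assumed missing shares. The period before Amendment 2 is a possible, unquantified source of missing conjunctivitis pages. No power, type I error or efficacy result is affected. This is a cheap improvement, not a threat to the trial's conclusions.

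**What to change.** Before unblinding:

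- In SAP 6.6.1, identify conjunctivitis, acne and folliculitis from all treatment-emergent AEs by a pre-specified preferred-term list or customized MedDRA query, as is already done for herpes zoster. Also keep any event that has a linked details page, so that cases confirmed by the investigator but coded elsewhere are not lost.
- Use the details pages for descriptive information such as type, treatment and resolution.
- Report by arm the number of term-identified events without a page, and the number of pages without a matching term. If the pages are complete, these counts will show it.
- Align Appendix 8.2.6 with the same case definition. Keep its merge for the details listings.

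The cost is SAP wording, a short review to settle the term list, and a little programming. No new data are needed and nothing changes in how participants are managed.

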6.6.2. Laboratory Data

Laboratory data will be listed and summarized in accordance with the CaPS reporting standards. Summaries of participants meeting pre-specified monitoring and discontinuation criteria will be created using methods for categorical data ([Section 5.2.4](#)).

6.6.3. Vital Signs

Vital signs will be summarized at Baseline and at Weeks 2, 4, 8, 12, 16, 20 and 26. Height will be reported at baseline only and weight will be summarized at baseline, Week 12 and Week 20.

6.6.4. Electrocardiograms

ECG parameters, if applicable, will be summarized at baseline and End of Treatment visits.

6.6.5. Physical Examination

Physical examinations will be summarized at the screening visit.

6.6.6. Suicide Severity Rating Scale (C-SSRS)

C-SSRS will be mapped to Columbia-Classification Algorithm of Suicide Assessment (C-CASA) categories. C-CASA will be summarized by number and percent at baseline and all-available post-baseline visits.

7. INTERIM ANALYSES

This study uses an External Data Monitoring Committee (E-DMC). The E-DMC will be responsible for ongoing monitoring of the efficacy and safety of participants in the study according to the charter. The recommendations made by the E-DMC to alter the conduct of the study will be forwarded to Pfizer for final decision. Pfizer will forward such decisions, which may include summaries of aggregate analyses of endpoint events and of safety data that are not endpoints, to regulatory authorities, as appropriate. Composition of the E-DMC and processes under which the E-DMC operates will be documented in the E-DMC charter.

9. APPENDICES

Appendix 1. Summary of Efficacy Analyses

Endpoint	Analysis Type	Population	Data Inclusion and Rules for Handling Intercurrent Events and Missing Data	Analysis Model
Week 2 PP-NRS4 Response	Main analysis	FAS with baseline PP-NRS ≥ 4	For participants who drop out for any reason or use rescue therapy, the response will be defined as “non-responsive” after that point.	CMH
	Sensitivity/supplementary analysis	FAS with baseline PP-NRS ≥ 4	For participants who drop out for any reason, the response will be defined as “non-responsive” after that point.	CMH
	Sensitivity/supplementary analysis	FAS with baseline PP-NRS ≥ 4	All observations will be used; missing values will be handled through multiple imputations.	CMH
Week 4 EASI-90 Response	Main analysis	FAS	For participants who drop out for any reason or use rescue therapy, the response will be defined as “non-responsive” after that point.	CMH
	Sensitivity/supplementary analysis	FAS	For participants who drop out for any reason, the response will be defined as “non-responsive” after that point.	CMH

Endpoint	Analysis Type	Population	Data Inclusion and Rules for Handling Intercurrent Events and Missing Data	Analysis Model
	Sensitivity/supplementary analysis	FAS	All observations will be used; missing values will be handled through multiple imputations.	CMH
Week 16 EASI-90 Response	Main analysis	FAS	For participants who drop out for any reason or use rescue therapy, the response will be defined as “non-responsive” after that point.	CMH
	Sensitivity/supplementary analysis	PPAS	For participants who drop out for any reason or use rescue therapy, the response will be defined as “non-responsive” after that point.	CMH
	Sensitivity/supplementary analysis	FAS	For participants who drop out for any reason, the response will be defined as “non-responsive” after that point.	CMH
	Sensitivity/supplementary analysis	FAS	All observations will be used; missing values will be handled through multiple imputations.	CMH
Weeks 2, 4, 8, 12, 16, 20 and 26 Percent Change from Baseline in %BSA	Main analysis	FAS	Data after dropout or use of rescue therapy will be set as missing; only observed data will be used.	MMRM
Time from baseline to achieve at least a 4-point	Main analysis	FAS with baseline	PP-NRS observations will first be censored by use of rescue therapy; for all participants who have not	Time to Event

Endpoint	Analysis Type	Population	Data Inclusion and Rules for Handling Intercurrent Events and Missing Data	Analysis Model
improvement in the severity of PP-NRS scale		PP-NRS ≥ 4	experienced the event, their time to event will be right censored at the last available measurement time.	
Medicated Topical Background Therapy-Free days	Main analysis	FAS	The intercurrent event is captured through endpoint definition. Missing dates will be imputed by Pfizer standards.	ANCOVA

CMH=Cochran-Mantel-Haenszel; ANCOVA=Analysis of Covariance; MMRM=Mixed-effect Model Repeated Measures; TP=Tipping Point.

PP-NRS4 Response at all other scheduled timepoints will follow the main analysis of Week 2 PP-NRS4 Response. Other binary endpoints will follow the main analysis of Week 4 EASI-90 Response.

Other percent change from baseline or change from baseline to each specific post baseline scheduled time points in a continuous outcome measure will follow the main analysis of Weeks 2, 4, 8, 12, 16, 20 and 26 Percent Change from Baseline in %BSA.

Appendix 2. Definition and Use of Visit Windows in Reporting

Unless otherwise specified, visit windows will be used for efficacy variables, and for any safety data that display or summarize by study visit. For other endpoints (eg, ECG, vital signs), visit windows will be applied for summary statistics by study visits if required.

Visit Label	Target Day	Definition [Day window]
Screening		Days -28 to Day -1
Baseline	Day 1 (Day of first dose), Baseline	Day 1
Week 2	15	Days 2 to 22
Week 4	29	Days 23 to 43
Week 8	57	Days 44 to 71
Week 12	85	Days 72 to 99
Week 16	113	Days 100 to 127
Week 20	141	Days 128 to 155
Week 24	169	Days 156 to 176
Week 26	183	Days 177 to 197
Follow Up/End of Study		
Week 30	-	Days 198 to -

If there are both observed records and missing records within the same visits window, the observed record will be used.

For the lab values, if the calculated study day for the labelled baseline visit is not study Day 1 but falls within 28 days before the start of the study dosing, then that data should be used for the baseline instead of leaving baseline missing.

For the other values, if the calculated study day for the labelled baseline visit is not study Day 1, but falls before the start of the study dosing, then that data should be used for the baseline instead of leaving baseline missing.

If two or more visits fall into the same window, keep the one closest to the Target Day. If two visits are equaled distant from the Target Day in absolute value, the later visit should be used.

If two or more values are collected on the same day: for measurements with labeled visits, the value where collect visit = analysis visit will be used; for measurements without labeled

visits but with time of collection, the last measurement of the day will be used for the analysis.

PP-NRS is recorded every day throughout the study. Observations on the actual day will be used to analyze Days 2-15 PP-NRS, and to derive the time to achieve PP-NRS4 response. Weeks 2, 4, 8, 12, 16, 20 and 26 PP-NRS response will be based on the windowing method.

Safety analysis may follow Pfizer standards.

For Estimand 1 and 2, data after rescue therapy will be censored first. The remaining observation will be mapped to the analysis visits.

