5.3. Methods to Manage Missing Data

5.3.1. Binary Endpoints

For binary endpoints analyzed at each scheduled timepoint separately, visit windows ([Appendix 2](#)) will be used to map all observed data into nominal visits. After mapping, missing data will be handled by one of the following methods.

Method 1: any observations missing intermittently (including baseline values) will be considered missing completely at random (MCAR) and will remain missing in the analysis. This method is based on Estimand 1 and Estimand 3.

Method 2: additional analyses will utilize the longitudinal nature of the binary endpoint. A Generalized Linear Mixed Model (GLMM) will be fit to all observed data (ie, regardless of rescue therapy and without defining missing data as “non-response”). The binary outcome will be modeled using a logistic-normal distribution. Fixed factors will include treatment (abrocitinib and dupilumab), visit (Weeks 2, 4, 8, 12, 16, 20, 26) and treatment-by-visit interaction. Visit will be modeled as a categorical covariate. A participant-specific random intercept will be used to model the correlation within a participant over time ([Appendix 3](#)). Missing observations will be multiply imputed under the assumption that the missing data mechanism is MAR. Using the estimated posterior predictive distribution of the GLMM model parameters obtained using Markov Chain Monte Carlo (MCMC) methods, estimates of the posterior predictive probability of response will be calculated for each treatment group. A single imputation of the missing value will be sampled from a Bernoulli distribution with the corresponding posterior predictive probability of response. This imputation will be repeated multiple times with different MCMC samples to obtain multiple completed datasets. For each such completed dataset, the estimates of the proportions and CMH-weighted difference of proportions between abrocitinib and dupilumab will be obtained along with the associated standard errors using the methods in [Section 5.2.1](#). Rubin’s rule (Rubin, 1987) will be used to combine the multiple estimates and standard errors across the imputed datasets and provide p-values. More detailed descriptions are provided in [Appendix 3](#).

Method 2 is based on Estimand 4 treatment policy estimand and will be used for the supplementary analysis of the primary and key secondary endpoints.

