6. ANALYSES AND SUMMARIES

A summary of analyses for clinical efficacy endpoints is provided in [Appendix 1](#). Visit windows to be used for all efficacy analyses and some relevant safety analyses are detailed in [Appendix 2](#).

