6.2.2. Secondary Endpoints

6.2.2.1. Binary Endpoints

- Endpoints:
 - Weeks 2, 8, 12, 20 and 26 EASI-90 Response;
 - Weeks 2, 4, 8, 12, 16, 20 and 26 EASI-75, IGA Response based on score of clear (0) or almost clear (1) (on a 5-point scale) and a reduction from baseline of ≥ 2 points;
 - PP-NRS4 Response each day from Days 2-15, Weeks 4, 8, 12, 16, 20 and 26.
 - Weeks 2, 12, 16, 20 and 26 DLQI ≥ 4 Points Improvement from Baseline Response
- Estimand strategy: Estimand 1, composite estimand.
- Analysis set: FAS ([Section 4](#)). Participants must have baseline PP-NRS ≥ 4 to be included in the analysis for PP-NRS4. Participants must have baseline DLQI ≥ 4 to be included in the analysis for DLQI response.
- Analysis methodology: CMH and normal approximation in [Section 5.2.1](#).
- Intercurrent events and missing data: The intercurrent event is captured through the variable definition; for participants who drop out for any reason or use rescue therapy, the response will be defined as "non-responsive" after that point.
- The number of participants, number and percent of response at each specified Weeks along with the 95% confidence interval by normal approximation will be presented for each treatment arm.

- The CMH test p-value, the estimate of the difference in proportions of response at each specified Weeks along with the 95% confidence interval by CMH normal approximation will be presented for abrocitinib versus dupilumab.

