6.2.2.2. Continuous Endpoints

- Endpoints:
 - Weeks 2, 4, 8, 12, 16, 20 and 26 Percent Change from Baseline in %BSA, SCORAD;
 - Weeks 12, 16 and 26 Change from Baseline in HADS;
 - Weeks 2, 12, 16, 20 and 26 Change from Baseline in DLQI;
 - Weeks 12, 16 and 26 Change from Baseline in EQ-5D-5L, POEM, MOS-Sleep Scale;
 - Weeks 2, 12, 16, 20 and 26 Change from Baseline in Skin Pain NRS.
- Estimand strategy: Estimand 2, hypothetical estimand ([Section 2.1.2](#)).
- Analysis set: FAS ([Section 4](#)). Participants must have observed baseline measure to be included in the corresponding analysis.
- Analysis methodology: MMRM ([Section 5.2.3](#)) including change from baseline or percent change from baseline data from the corresponding weeks.
- Intercurrent events and missing data: drop-out for any reason and use of rescue therapy are the intercurrent events; data after dropout or use of rescue therapy at any time during the treatment period will be set as missing; only observed data will be used.
- Number of participants included in the analysis will be presented for each treatment arm.
- The least square mean (LSM) of change from baseline or percentage change from baseline along with the corresponding 95% confidence interval will be presented for each treatment arm at each specified time points.
- The LSM difference along with the corresponding p-value and 95% confidence interval will be presented for abrocitinib versus dupilumab at each specified time points.

6.2.2.3. Time from baseline to achieve at least a 4-point improvement in the severity of PP-NRS scale

- Analysis set: FAS (Section 4). Participants must have baseline PP-NRS ≥ 4 to be included.
- Analysis methodology: analysis of time to event endpoint (Section 5.2.5).
- Intercurrent events and missing data: PP-NRS observations will first be censored by use of rescue therapy; for all participants who have not experienced the event, their time to event will be right censored at the last available measurement time.
- The number of participants, number and percent of participants censored and participants with PP-NRS4 Response will be provided for each treatment arm.
- Estimated survival curves using the Kaplan-Meier method and number of patients at risk will be displayed graphically for each treatment arm. The 25%, 50% and 75% quartiles with their 95% confidence intervals will also be presented for each treatment arm.

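### SAP Appendix 2 gives clinic measures a Week 24 window that no by-visit efficacy analysis reads, so a few late-discontinuation or early Week 26 records go unused

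*SAP*

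**What the plan says.** **Scope of the windows.** SAP Appendix 2 says that, unless otherwise specified, "visit windows will be used for efficacy variables, and for any safety data that display or summarize by study visit". SAP Section 6 repeats this ("Visit windows to be used for all efficacy analyses and some relevant safety analyses are detailed in" Appendix 2), and Section 5.3.1 says that for binary endpoints the windows "will be used to map all observed data into nominal visits".

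**The three late windows.** Week 20 (target Day 141) is "Days 128 to 155", Week 24 (target Day 169) is "Days 156 to 176", and Week 26 (target Day 183) is "Days 177 to 197". When two visits share a window, the one nearer the target day is kept. No rule moves a record to a different window. The preference for the value whose collected visit matches the analysis visit applies only to values taken on the same day.

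**What happens at Week 24.** Protocol Section 1.3 makes Week 24 a call. EASI, BSA, SCORAD, IGA, DLQI and Skin Pain NRS are marked at Week 20 and at the Week 26 end-of-treatment/early-discontinuation visit, but not at Week 24.

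**What is analysed.** Section 6.2.2.1 lists "Weeks 2, 8, 12, 20 and 26 EASI-90 Response", and Section 6.2.2.2 lists "Weeks 2, 4, 8, 12, 16, 20 and 26 Percent Change from Baseline in %BSA, SCORAD". The imputation model in Section 5.3.1 and Appendix 3 has seven visits, none of them Week 24. Vital signs (Section 6.6.3) also skip Week 24.

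**When clinic records can arise there.** Protocol Section 7.2 asks for an early-discontinuation visit when a participant leaves. Section 7.3 places the end-of-treatment visit within a week of the last dose. Either can fall on any study day.

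**The concern.** A clinic record dated Day 156 to 176 is labelled Week 24 and then used at neither Week 20 nor Week 26. The likely sources are participants who stop treatment late and, less often, a Week 26 visit held well ahead of schedule. The MMRM loses an observed value. An early-seen completer has no Week 26 value. The imputation model, which is meant to use all observed data, has no category for the record.

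The label brings these measures no benefit, since none of them is scheduled or reported at Week 24. The SAP also treats its two telephone contacts differently without giving a reason. Week 1 is a call too, but it has no window row, and the Week 2 window simply starts at Day 2.

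**Working it through.** **1. Reproduce the stated windows.** Inputs are the target days in Appendix 2, plus Day 211 for Week 30 from the Schedule of Activities. Rule: a window ends at the midpoint between its target and the next one, and the following window starts the day after.

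- Week 2: (15 + 29)/2 = 22
- Week 4: (29 + 57)/2 = 43
- Week 8: (57 + 85)/2 = 71
- Week 12: (85 + 113)/2 = 99
- Week 16: (113 + 141)/2 = 127
- Week 20: (141 + 169)/2 = 155
- Week 24: (169 + 183)/2 = 176
- Week 26: (183 + 211)/2 = 197

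All eight upper limits match Appendix 2. The Week 24 window follows the SAP's own rule; it exists because Day 169 is kept as a target.

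**2. Same rule without Day 169.** (141 + 183)/2 = 162. Week 20 becomes Days 128–162 and Week 26 Days 163–197. Of the 21 days now labelled Week 24, 7 (Days 156–162) go to Week 20 and 14 (Days 163–176) go to Week 26.

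**3. Which of those days help.** A record on Days 156–162 competes with the scheduled Week 20 visit (Day 141 ± 3, so Days 138–144) and normally loses under the nearest-to-target rule. The practical gain is therefore on Days 163–176.

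**4. Size.** Assumption: 8–15% of 600 drop out, evenly over 26 × 7 = 182 days. The documents give neither a rate nor a pattern.

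- Records labelled Week 24: 600 × 0.08 × 21/182 = 5.5, to 600 × 0.15 × 21/182 = 10.4.
- Records usefully recovered: 600 × 0.08 × 14/182 = 3.7, to 600 × 0.15 × 14/182 = 6.9. That is about 4–7 participants over both arms.

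**5. Early completers.** The protocol window for Week 26 is Day 183 ± 3, so Days 180–186. A record is lost only on Day 176 or earlier, at least 180 − 176 = 4 days before that window opens.

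**6. Distance from target after the change.** A Week 26 value could be up to 183 − 163 = 20 days early. A Week 20 value could be up to 162 − 141 = 21 days late.

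**The case against.** Several counter-arguments are sound and limit the point.

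- **Week 24 is not the only gap.** A reader might infer that drop-outs at any other time keep their last assessment. They do not. An early-discontinuation visit on Day 65 shares the Week 8 window with the Day 57 visit and is discarded. HADS, POEM, EQ-5D-5L and MOS-Sleep are analysed only at Weeks 12, 16 and 26, so their records on Days 2–71 and 128–155 also go unread. DLQI and Skin Pain NRS have the same gap on Days 23–71.
- **Composite handling.** Under Estimand 1 a drop-out is a non-responder from that point. With wider Week 26 limits and nothing else, someone who left on Day 165 with EASI-90 could be counted as a Week 26 responder. This stands, and the fix must include a guard.
- **Harm to the missing-at-random assumption.** A reader might infer that losing these records undermines the Week 26 MMRM. The documents do not show this. The affected participants would normally have a Week 20 value for EASI, SCORAD or BSA, and the model uses the values for the endpoints it analyses.
- **Dating of drop-out.** SAP Section 4 censors observations after drop-out. If drop-out is dated at the last dose, an end-of-treatment visit up to a week later may be censored whatever its window.
- **Early completers.** Treating their missing Week 26 value under Method 1 is an inference, because Method 1 speaks of intermittent gaps and Week 26 is the last treatment-period visit.

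None of this explains why clinic measures need a Week 24 label, or why the Week 1 call is handled differently.

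**Conclusion.** The point holds as a cheap improvement. One window table serves all efficacy variables and sends clinic records from Days 156–176 to a visit that no by-visit efficacy analysis reads. Time to PP-NRS4 uses actual days, and the therapy-free-days endpoint may use dated EASI records, but neither relies on the Week 24 label.

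The effect is on Week 26 secondary endpoints, for which the SAP makes no controlled significance claim. The gain is about 4–7 participants under the assumed 8–15% even drop-out, fewer if drop-out is dated at the last dose, plus any completer seen by Day 176. With the guard in place, drop-outs gain nothing in the Estimand 1 binary analyses, so their benefit is in the MMRM.

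A reader might infer that the primary or key secondary results are at risk. They are not: the main analyses at Weeks 2, 4 and 16 use other windows, and the supplementary imputation model is touched only indirectly, through its Week 26 data.

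**What to change.** In SAP Appendix 2:

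1. For clinic measures collected at Weeks 20 and 26 but not at Week 24 (EASI, IGA, SCORAD, BSA, DLQI, Skin Pain NRS), delete the Week 24 row and set Week 20 = Days 128–162 and Week 26 = Days 163–197. Keep the Week 24 row only for data collected at that call.
2. State that data after drop-out or rescue are censored before mapping, as each estimand requires, and say how drop-out is dated. Appendix 2 now gives this order only for rescue, under Estimands 1 and 2.
3. State that under Estimands 1 and 3 a participant who dropped out before Week 26 stays a non-responder at Week 26, whatever an earlier discontinuation record shows.

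The cost is two window limits and two sentences. The downside is that a few Week 26 values may lie up to 20 days before target. Week 2 already accepts Day 2 for a Day 15 target, a distance of 13 days. HADS, POEM, EQ-5D-5L and MOS-Sleep are not analysed at Week 20, so this change does not cover them.
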